After pre-testing in each healthcare system, the enhanced EHR functionalities will be implemented in experimental clinics as they become available for induction into the study starting with the two pilot experimental clinics that are identified by the health systems. During the 6-month period when the enhanced EHR resources are being developed (anticipated completion 1/10/15), candidate clinics will be screened for participation criteria as noted above.

**Assignment to conditions.** Clinics will be assigned in sets or groupings using a multistage or captive assignment procedure. These sets can vary in size, and not all members of a set must be available for assignment at the same time. We propose that assignment may start when there are at least 3-6 clinics available for assignment. The clinics in each set will be randomly assigned until the set is exhausted, and then clinics within the next set will be assigned. Within each set of clinics, a subset will be assigned to the control condition and a subset will be assigned to the experimental condition to ensure that assignment to condition is not correlated with time and secular events (as the sets will be started at different times as additional clinics become available). Finally, we will use an approximation to the MultiAttribute Utility Measurement (MAUM) strategy using principal components (PC’s) to stratify clinics with regards to possible biasing features: size, mix of Medicaid patients, healthcare system, and

“Breaking Addiction to Tobacco for Health (BREATHE) Study”

PI: [name], MPH, MBA; UW-CTRI Center Grant: 1P01CA180945-01.

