rural-urban setting, baseline rate of WTQL referral, and smoker prevalence. These criteria can be altered depending upon their pre-assignment availability. Thus, the approach involves: 1) Conducting a PC analysis in the pool of *potentially* available clinics (combined across the 2 healthcare systems) to identify a small number of uncorrelated PC's. 2) Integrating the PC's in a way that reflects the hypothesized direction of their impact on outcomes (inflating vs. reducing treatment engagement). 3) Locating all clinics available for randomization on a single dimension that reflects the hypothesized net impact of the PC's. 4) Forming two groupings of high and low clinics that are set using a cut-score imposed on the dimension composite. 5) The clinics are randomly assigned within and across sets in a manner that ensures that approximately an equal number of high and low ranking clinics are assigned within each condition. Thus, if a set of 6 clinics is being used for captive assignment, and this entails assigning 2 of the 6 to the control condition, one of the high scoring clinics and one of the low-scoring clinics will be randomly assigned to the control condition. Conversely, 2 of the high scoring and 2 of the low-scoring clinics must be assigned to the experimental condition (to complete an assignment set), exhausting this particular set. Thus, randomization to condition is nested within the high and low PC-score groupings. We will assign clinics to the two conditions on a 50/50 basis during early recruitment when the ultimate N (and mix of experimental and control clinics is unknown). Note that if the set of clinics is quite small (due to limited availability at a given point in time), it might be the case that only one clinic can be assigned to a particular condition in that set (e.g., to the control condition). In that case, in the next set the clinic assigned to the control condition must come from the other end of the PC risk dimension. In this way, the approach is flexible but nevertheless increases the likelihood that clinics are assigned to the two conditions at a similar rate over time, and that the two conditions are similarly balanced on factors thought to affect the dependent variables.

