**Clinic Randomized Control Trial**

“Breaking Addiction to Tobacco for Health (BREATHE) Study”

PI: [name], MPH, MBA; UW-CTRI Center Grant: 1P01CA180945-01.

The primary outcome will be treatment engagement and we will analyze this with repeated measures analysis of variance (ANOVA) and analysis of covariance (ANCOVA). In these analyses we will contrast the experimental and control (F2Q) clinics on the basis of treatment engagement means averaged over the periods of clinic participation (which may differ somewhat across clinics) pre and post implementation. Since data on the dependent variables will be routinely collected pre-implementation, we have opportunity to determine the length of the baseline period: we will average data over 6 months to establish a baseline. The analyses will, conservatively, use the clinic as the unit of analysis. ANCOVA will use clinic location (rural vs. urban), size, SES, and baseline rates of smoker documentation and referral as covariates. We will conservatively use ANOVA to estimate power, in part, because it is unclear how much this set of covariates will affect error within the ANCOVA. Based on earlier data, we anticipate treatment engagement will be 1% for both groups at baseline (for the 6 months pre-implementation) and 10 and 2% post-implementation for experimental and control clinics, respectively. Previous research also suggests that both groups will have the same standard deviation (SD = 4). Assuming an SD = 4, and a mean difference of 8 at post-implementation (2% vs 10%), power to detect a group by time interaction  $> .998$  with  $\alpha = .05$  and  $N = 28$  (18 experimental and 10 control clinics). If we are able to recruit adequately with only 10 experimental clinics (with  $N = 20$ , comprising 10 experimental and 10 control clinics), the smallest  $N$  that we can envision, then power = .887 with a smaller prognosticated post-implementation group difference (8 vs. 2%). Thus, power appears ample for conservative tests of our primary outcome. We will use other analytic strategies to analyze these data (e.g., General Estimating Equations) that model patients as the units of analysis, with patients being nested within clinics. Only aggregated (non-identifiable) data will be used for these analyses. Such approaches should have greater power than the approach described above, which we present for purposes of clarity and simplicity. In addition, in secondary analyses we will compare subcategories of treatment engagement rates: e.g., comparing WTQL engagement rates in the control clinics with engagement rates for *cessation* treatment in the experimental clinics (i.e., removing chronic care engagement data for smokers who wanted to reduce their smoking). We will also examine treatment completion rates and 6-month abstinence rates, especially for those referred to the chronic care treatment, to determine the “yield” of treatment referral. Such data would also allow us to compute cost-effectiveness and cost-benefit analyses.

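### Clinic randomised trial: the status of two pilot experimental clinics is not stated, no single primary test is named, and neither candidate test includes the randomisation stratum or adjusts for baseline engagement as a covariate

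*Combined protocol and SAP*

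**What the plan says.** **Assignment.** In Study Design, Clinic Randomized Control Trial, the enhanced record functions go into experimental clinics as these become available, "starting with the two pilot experimental clinics that are identified by the health systems". The pilots are not mentioned again. The next paragraph, on assignment to conditions, states a general rule with no exception: "Clinics will be assigned in sets or groupings using a multistage or captive assignment procedure". Each set contains both conditions "to ensure that assignment to condition is not correlated with time and secular events". Clinics are scored on a principal-component (PC) composite and cut into high and low groups, so that "randomization to condition is nested within the high and low PC-score groupings".

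**Analysis.** In the power section for the clinic trial, the plan says of the primary outcome, treatment engagement: "we will analyze this with repeated measures analysis of variance (ANOVA) and analysis of covariance (ANCOVA"). It adds that "we will contrast the experimental and control (F2Q) clinics on the basis of treatment engagement means averaged over the periods of clinic participation", before and after implementation. The adjusted model is given as: "ANCOVA will use clinic location (rural vs. urban), size, SES, and baseline rates of smoker documentation and referral as covariates". ANOVA is chosen for the power calculation, but neither method is called primary. Models with patients nested in clinics are mentioned as further strategies.

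**Power.** The figures are described as "power to detect a group by time interaction": above .998 for 18 experimental and 10 control clinics (difference 8 points, SD 4), and .887 for 10 and 10 (difference 6 points).

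**The concern.** **Pilots.** If the health systems chose these two clinics and they went straight into the experimental arm, the primary contrast is not fully randomised. A health system may well nominate clinics that are keen or well organised. A stable difference in level would cancel in a group-by-time test. A stronger response to the intervention would not, and it would be credited to the intervention.

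**Primary test.** Two unranked tests of one primary outcome leave room to choose after the data are seen.

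**Model and design.** Randomisation is balanced within the high/low PC groups, but neither model contains that grouping. Baseline engagement, the outcome's own baseline, serves only as the pre measure in the ANOVA; the ANCOVA list has baseline documentation and referral instead. With 20 to 28 clinics as units, these choices affect precision and how well the test keeps its nominal level.

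**Working it through.** **Inputs from the power section:** clinic as unit, SD 4 in both groups, alpha .05 (two-sided reproduces the figures), 18:10 with difference 8, 10:10 with difference 6.

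**1. The stated power.** Two-sample t-test, noncentrality = d / [SD × √(1/nE + 1/nC)], df = nE + nC − 2.
- 18:10: 8 / [4 × √(1/18 + 1/10)] = 5.07, df 26, power .998.
- 10:10: 6 / [4 × √(1/10 + 1/10)] = 3.35, df 18, power .887.

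Both figures reproduce as a post-only comparison with SD 4. Without the pilots the same test gives:
- 16:10: noncentrality 4.96, df 24, power .997.
- 8:10: noncentrality 3.16, df 16, power .843.

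**2. Effect of non-randomised pilots.** The documents give no pilot excess, so 2, 4 and 8 points are assumed. Inflation of the experimental mean = (2/nE) × excess. The false-positive rate is simulated with error SD 4 and no true effect elsewhere.

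| Assumed excess | Inflation 18:10 | Inflation 10:10 | False positives 18:10 | False positives 10:10 |
|---|---|---|---|---|
| 2 | .22 | .40 | .049 | .053 |
| 4 | .44 | .80 | .051 | .060 |
| 8 | .89 | 1.60 | .052 | .078–.079 |

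**3. Two unranked tests.** I simulated the null case for the group-by-time test and a post-score ANCOVA on five uninformative covariates. Each rejects about 5% of the time. Claiming success if either is significant rejects about .07 to .08 with an assumed baseline SD of 1, and about .09 with 4, at both 10:10 and 18:10. This is an upper illustration: the plan does not propose an either-test rule, but it does not exclude one.

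**4. Omitted stratum.** Assume a 4-point engagement gap between high and low clinics, SD 4 within stratum, 10:10, difference 6. With the stratum in the model, the false-positive rate is .05 and power .88. Without it, they are about .03 and .82 to .83. The test stays valid but becomes conservative.

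**5. Group-by-time power at the minimum size.** SD of change = √(16 + sB² − 2 × r × 4 × sB), where sB is the SD of baseline engagement and r the pre-post correlation. The plan states neither. Results at 10:10, difference 6:

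| Assumed sB | r=.1 | r=.25 | r=.4 | r=.5 |
|---|---|---|---|---|
| 0.5 | .890 | .901 | .912 | .919 |
| 1 | .883 | .906 | .927 | .940 |
| 2 | .841 | .887 | .930 | .955 |
| 4 | .657 | .736 | .825 | .887 |

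**6. Power of the proposed ANCOVA** (arm, baseline engagement, balanced stratum; df N − 4; simulated with chance baseline imbalance). It does not depend on sB.

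| | r=.1 | r=.25 | r=.4 | r=.5 |
|---|---|---|---|---|
| 10:10 | .865 | .881 | .914 | .939 |
| 8:10 | .813 | .833 | .872 | .904 |

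**The case against.** **The pilots may be randomised.** The assignment paragraph states no exception, and a set may fill over time, so the pilots could belong to the first set. This stands: a reader might infer that they bypassed randomisation, but the documents do not say so. The gap is that their status is left open while the primary contrast takes in every experimental clinic.

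**The pilot harm is small and assumed.** This also stands. The highest rate, about .08, needs an excess of 8 points, as large as the full expected difference, together with the smallest trial the plan envisages.

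**The listed covariates already cover much of the stratum.** Location, size, socioeconomic status and baseline referral match or approximate four of the six features in the PC composite. That is fair for the ANCOVA but not for the ANOVA. Healthcare system, smoker prevalence and the grouping itself remain outside both.

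**The power figures are not fragile.** A reader might infer that the stated power holds only at a pre-post correlation of .5, or that group-by-time power depends strongly on that correlation. Both readings need a baseline SD of 4. The plan states SD 4 as equal between groups and applies it to a post-implementation difference; it does not say the SD is equal over time. It also expects baseline engagement of 1%. With 20 clinics averaging 1% and no negative rates, the largest possible SD is √[(19² + 19 × 1²)/19] = 4.47 (one clinic at 20%, the rest at zero), so 4 is implausible. At a baseline SD of 0.5 to 1, group-by-time power is .88 to .94, about equal to the proposed ANCOVA. The case for ANCOVA is therefore agreement with the design and independence from the baseline SD, not a large gain in power.

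**Conclusion.** The concern holds as a matter of incomplete specification, and the plan should be amended. Three gaps are plain on the page: the pilots' randomisation and analysis status, the absence of a named primary test, and a covariate list that omits both the randomisation stratum and baseline engagement.

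The size is modest. Analysing non-randomised pilots is negligible at 18:10 and small at 10:10, and that result rests on assumed excesses. Leaving out the balanced stratum does not bias the test; it costs precision only if the stratum predicts engagement. The arithmetic of the stated power is correct for a post-only test. What is missing is the baseline SD and correlation needed to carry it over to the group-by-time test at the minimum size. At 18:10 power is ample under every assumption examined: at least .95 even with baseline SD 4 and r = .1.

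**What to change.** 1. State how the two pilot clinics are assigned. Define the primary analysis as randomised clinics only, and add any non-randomised pilots in a sensitivity analysis.
2. Name one primary test: ANCOVA of post-implementation engagement on arm, baseline engagement and the high/low PC stratum. Keep the group-by-time ANOVA and the ANCOVA with the five listed covariates as sensitivity analyses.
3. Restate power at the minimum size for the clinics actually analysed, giving the assumed baseline SD and pre-post correlation.

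An induction-date term is optional, because the sets already mix the two conditions over time.

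**Cost.** Only the analysis wording changes, and no new data are needed. Up to two experimental clinics leave the primary contrast, and two degrees of freedom go to baseline and stratum. At 8:10 the ANCOVA has power of about .81 to .87 for r = .1 to .4, below the stated .887 unless r is about .45 or more. Moving the five covariates to a sensitivity analysis gives up whatever variance they explain, but on their own they would leave only 20 − 2 − 5 = 13 residual degrees of freedom at the minimum size.

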**Clinic Randomized Control Trial**

A set of EHR modifications (described in detail below) will be presented sequentially to groups of clinics within both healthcare systems as per an RCT design (RCT). Over 36 months, and across the two healthcare systems, the EHR enhancements will be introduced into up to 18 “experimental” clinics. During this time 10 control clinics will also be inducted into the study. It is possible that fewer experimental clinics will be used in this design if recruitment for Projects 2-4 is so successful that not all 18 clinics are required. The experimental clinics will each participate in the study for at least 16 months (albeit, unforeseen events could cause us to terminate participation earlier in some clinics: e.g., clinic closure, dramatic change in clinic size or structure). Experimental clinics will be yoked to a control clinic for the purpose of fixing the duration of participation. A variation of the Multiattribute Utility Measurement Matching strategy will be used to allocate experimental and control clinics so that they are matched with regard to key baseline variables and timing of study induction.

“Breaking Addiction to Tobacco for Health (BREATHE) Study”

PI: [name], MPH, MBA; UW-CTRI Center Grant: 1P01CA180945-01.

The following will serve as dependent variables: 1) rate of smoking status documentation among adult patients visiting the primary care clinic; 2) rate of referral of smokers to smoking treatment; and 3) rate of engagement in smoking treatment (the primary outcome).

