A set of standard EHR modifications will be implemented in (up to) 18 experimental clinics as part of the RCT. Importantly, these 18 clinics will also serve as recruitment sites for participants for Projects 2, 3, and 4, consistent with the integration of all projects across the P01. The ultimate, specific N for the experimental group may comprise 10–18 clinics depending on recruitment rates; we project good power across this range of sample size. The clinics participating in the study will be selected based on the following criteria: 1) *Size*: clinics will be fairly large, including at least 3-6 clinicians, to ensure adequate recruitment for the three clinical research projects. 2) *Location*: clinics will be concentrated in Southcentral and Southeastern Wisconsin so that case managers from UW-CTRI Madison and Milwaukee research sites can provide services at multiple clinics. 3) *Diversity*: clinics from both of the health systems will include both urban and rural location and a range of SES (based on rates of Medicaid and uninsured patients). 4) *Independence*: we will ensure that clinics with high levels of clinic integration (e.g., sharing significant numbers of staff) do not participate (i.e., only one of such highly linked clinics can participate). And, 5) all clinics will have to have, or be willing to adopt, the control or experimental smoker identification and referral routines (either fax referral or the enhanced EHR strategies) and be willing and able to collect necessary data.

The key new EHR functions that will be implemented and tested are: 1) a modified “**screen for smoking status**” to enhance the identification and documentation of all smokers visiting targeted primary care clinics; 2) an outreach to smokers, (direct-to-consumer communications) about the study availability in their clinic; 3) a **1-click referral system** to evidence-based smoking treatment with UW-CTRI case managers; 4) a **closed-loop feedback feature to communicate to the clinician the fate of a referral**, documenting receipt of the referral and treatment engagement; and 5) **EHR-based communication options** to inform smokers of treatment resources.

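### If more than 10 experimental clinics are used, the early 50/50 phase ties clinic assignment to induction time, and the primary contrast does not adjust for it

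*Combined protocol and SAP*

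**What the plan says.** Under Study Design, Clinic Randomized Control Trial, the protocol states that over 36 months "the EHR enhancements will be introduced into up to 18" experimental clinics, and "During this time 10 control clinics will also be inducted into the study". The same section adds: "The ultimate, specific N for the experimental group may comprise 10–18 clinics", depending on recruitment rates.

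Under Assignment to conditions, clinics are randomised in sets. Each set is to contribute clinics to both conditions, and the stated purpose is "to ensure that assignment to condition is not correlated with time and secular events". A worked example takes a set of six and says "this entails assigning 2 of the 6 to the control condition", which leaves four experimental. The text then adds: "We will assign clinics to the two conditions on a 50/50 basis during early recruitment", because the final number and mix are not yet known. It closes with a softer claim, that the approach "increases the likelihood that clinics are assigned to the two conditions at a similar rate over time".

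The primary analysis is described in the power section for the clinic trial. It will "contrast the experimental and control (F2Q) clinics on the basis of treatment engagement means averaged over the periods of clinic participation", before and after implementation, with the clinic as the unit. The ANCOVA covariates are location, size, SES, and baseline documentation and referral rates. Assignment set, induction date and calendar period are not among them.

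**The concern.** Putting both conditions in every set keeps assignment unrelated to time only if the experimental-to-control ratio is the same in every set. The plan starts at 1:1 and may finish at up to 18:10. The number of controls is fixed at 10, so every experimental clinic beyond the tenth raises the experimental share of the later sets. Experimental clinics then start later on average than controls.

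The pre-post comparison removes stable differences between clinics. It does not remove a change over the induction period in how much engagement rises after implementation, for example from changes in quitline services or EHR practice. In a pooled contrast such a change falls unequally on the two arms and is counted as part of the intervention effect. The plan applies the same approach to smoker documentation and treatment referral.

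**Working it through.** **Inputs.** From the Clinic Randomized Control Trial parts of the design and power sections: 10 control clinics; 10 to 18 experimental clinics; a 1:1 start of unstated length; SD 4 percentage points in both groups; difference 8 (10% v 2%) at 18:10; difference 6 (8% v 2%) at 10:10; alpha .05, taken as two-sided. Assumed here, because the documents give no figure: the number k of clinics assigned 1:1 (8, 12 or 16), and the shift S in engagement gain between early and late clinics (2 points, range 1 to 4).

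**1. The plan's own power.** A two-sample t-test with the noncentral t distribution gives .998 for 18:10, difference 8 (plan: above .998), and .887 for 10:10, difference 6 (plan: .887). Both figures reproduce.

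**2. The forced later ratio.** With k clinics at 1:1 and a final 18:10, late experimental = 18 − k/2 and late control = 10 − k/2. The late share of each arm is that number divided by 18 or by 10.

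| k at 1:1 | Remainder (exp:control) | Experimental share of remainder | Late share, experimental | Late share, control | Difference |
|---|---|---|---|---|---|
| 8 | 14:6 | 70% | 14/18 = .78 | 6/10 = .60 | .18 |
| 12 | 12:4 | 75% | 12/18 = .67 | 4/10 = .40 | .27 |
| 16 | 10:2 | 83% | 10/18 = .56 | 2/10 = .20 | .36 |

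The overall share is 18/28 = 64%. The correlation (phi) between early/late phase and condition is .19, .26 and .34. At 10:10 the remainder is always 1:1 and the correlation is zero.

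**3. Bias of the pooled contrast.** Bias = S × difference in late share.

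| k | S = 1 | S = 2 | S = 4 |
|---|---|---|---|
| 8 | 0.18 | 0.36 | 0.71 |
| 12 | 0.27 | 0.53 | 1.07 |
| 16 | 0.36 | 0.71 | 1.42 |

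**4. Type I error.** This is the unadjusted two-sample t-test at 18:10, SD 4, with no true effect, from 400,000 simulated trials per cell.

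| k | S = 1 | S = 2 | S = 4 |
|---|---|---|---|
| 8 | 5.0% | 5.0% | 4.8% |
| 12 | 5.1% | 5.5% | 6.6% |
| 16 | 5.4% | 6.5% | 9.8% |

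**5. Power when the contrast is made within phases.** Information = sum over phases of nE·nC/(nE+nC); SE = 4/√information; df = 28 − 3 = 25. Pooled information is 18×10/28 = 6.43.

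| k | Information | SE | Power, difference 8 | Power, difference 6 |
|---|---|---|---|---|
| pooled, unadjusted | 6.43 | 1.58 | .998 | .955 |
| 8 | 16/8 + 84/20 = 6.20 | 1.61 | .998 | .948 |
| 12 | 36/12 + 48/16 = 6.00 | 1.63 | .997 | .942 |
| 16 | 64/16 + 20/12 = 5.67 | 1.68 | .995 | .929 |

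Using the sets themselves costs little more. Two sets of 3:3 plus four sets of 3:1 give information 2×1.5 + 4×0.75 = 6.0 with df = 28 − 7 = 21, and power .997 for a difference of 8.

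**The case against.** The strongest reply is that the problem is conditional and small. The plan allows 10:10, where nothing drifts. The worked 4:2 set is 67% experimental, close to the overall 64%. Condition is still randomised within each mixed set, and the design section names timing of induction among the matching aims. The two pilot experimental clinics start first; if they count among the 18, they offset part of the drift. The plan also expects control clinics to gain only 1 point in total (1% to 2%), so an early-late shift of 2 to 4 points is large by the plan's own figures.

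Most of this stands and limits the size of the point. It does not remove it. Matching on timing is an aim that the set procedure cannot deliver once the ratio shifts. The length of the 50/50 phase is not defined, and no term in the primary analysis corrects for the shift.

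A reader might go further and infer that the last experimental clinics would have no concurrent control, because all 10 controls could be used in the first 20 clinics, leaving 8:0. The documents do not support this. Such a tail would break the rule that every set holds both conditions, and the 10 v 10 design in the power section is an alternative smaller trial, not the first 20 clinics of a larger one. Even in that case earlier controls could still be in follow-up: assuming even spacing and 16 months of control participation, the last control overlaps each of the last eight experimental clinics by at least 5.3 months. Nor does the procedure achieve the reverse of its aim, since a phi of .19 to .34 is a partial association.

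**Conclusion.** The point holds in a limited form. If more than 10 experimental clinics are used with 10 controls, the 50/50 start makes assignment correlated with induction time, so the claim that the procedure will "ensure" otherwise is too strong, and the pooled primary contrast leaves the imbalance unadjusted. The ratio shift is arithmetic and needs only a 1:1 start and a final mix above 10:10.

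The size of the bias rests on assumptions about k and S. At 18:10 with 8 to 16 clinics assigned 1:1, a 2-point shift moves the contrast by 0.36 to 0.71 points, with type I error of about 5% to 7%. Over shifts of 1 to 4 points the range is 0.18 to 1.42 points, with type I error up to about 10%. None of this would overturn a true effect near the planned 8 points. It matters more if the true effect is small, and it affects the estimate and its interval in any case. The stated power figures are sound. The documents do not say whether the two pilot clinics are randomised or counted among the 18.

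**What to change.** In the clinic-trial analysis, make the primary contrast within assignment sets, with set as a fixed factor, or induction phase where sets are very small. This analyses clinics by the groups within which they were randomised.

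Under Assignment to conditions, keep the 50/50 start, state when it ends, and hold back at least one control place for every later set. The both-conditions rule already requires this, and a set with only one condition would contribute nothing to a within-set contrast.

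The cost is a few degrees of freedom. Power at 18:10 is about .995 to .998 for a difference of 8 (.998 unadjusted) and .93 to .95 for a difference of 6 (.955 unadjusted).

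A fixed 18:10 ratio from the first set is not recommended. If recruitment stopped at 10 experimental clinics, 10 × 10/18 = 5.6, so only 5 or 6 controls would be in place. Power for a difference of 6 would then be about .72 or .77 instead of .887. The 50/50 start protects that smaller design.
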